5.3. Secondary Endpoint(s) Analyses

5.3.1. Efficacy Endpoints / Variables

- Changes in Subject's energy and stamina as evidenced on the Fatigue Assessment form.
- Changes in Visual Analog Scale of non -Neurological Symptoms. The symptoms included in this scale are (1) dyspnea a rest and with activity, (2) cough, (3) body aches, and (4) joint pain.
- Changes in Subject's quality of life as evidenced by the Short Form 36 Health Survey Questionnaire.
- Changes in Subject's level of depression as evidenced by the PHQ 9 scale.

Primary analysis

Primary analysis of Repeated Measures Analysis (RMA) Model will be performed for above secondary efficacy endpoints above as given in the Section 5.2.2.

Secondary analysis

Secondary analysis of ANCOVA model will be perfored to test the significance of treatment difference for secondary efficacy endpoints above as given in the Section 5.2.2.

Additional analysis

Additional analysis of paired comparison will be performed using paired t-test to check for statistical significance will be performed for above secondary efficacy endpoints above as given in the Section 5.2.2.

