Duration of administration	1 hour
Laboratory Samples.	Screening, Week 0, 6, and 26.

	Screening
Visits by Weeks	Week 0 _ Infusion 1
	Week 2 _ Infusion 2
	Week 6 _ Infusion 3
	Week 10 _ Infusion 4
	Week 14 _ Follow Up 1
	Week 20 _ Follow Up 2
	Week 26 – End of Study

“A randomized, double-blinded, single-center, phase 2 efficacy, and safety study of allogeneic HB-adMSCs for the treatment of patients with Chronic Post-COVID-19 Syndrome.”

Objectives

Primary Objectives

- To investigate the efficacy of intravenous infusions of HB-adMSCs (allogeneic) vs. Placebo in patients with Chronic Post-COVID-19 Syndrome as determined by improvements in individual symptom scores of Visual Analog Scale of Neurological Symptoms. (Time frame: Baseline to Week 26).
- To assess the safety of intravenous infusions of HB-adMSCs (allogeneic) vs. Placebo in patients with Chronic Post-COVID-19 Syndrome as determined by the incidence of adverse events or serious adverse events (Time frame: Baseline to Week 26).

Secondary Objectives

- To investigate the efficacy of intravenous infusions of HB-adMSCs (allogeneic) vs. Placebo in patients with Chronic Post-COVID-19 Syndrome as determined by improvements in individual symptom scores of Visual Analog Scale of Non-Neurological Symptoms. (Time frame: Baseline to Week 26).
- To evaluate the efficacy of intravenous infusions of HB-adMSCs (allogeneic) vs. Placebo in patients with Chronic Post-COVID-19 Syndrome as determined by changes in Fatigue Scale (Time frame: Baseline to Week 26).
- To assess the efficacy of intravenous infusions of HB-adMSCs (allogeneic) vs. Placebo in patients with Chronic Post-COVID-19 Syndrome as determined by changes in SF-36 Quality of life self-assessment. (Time frame: Baseline to Week 26).
- To identify the safety of intravenous infusions of HB-adMSCs vs. Placebo in patients with Chronic Post-COVID-19 Syndrome as determined by changes in Patient Health Questionnaire (PHQ-9).

Endpoints

Primary Endpoints

The efficacy and safety primary endpoints of this study will be evaluated by assessing changes from Baseline to Weeks 26 in the following:

- Visual Analog Scale of Neurological Symptoms. VAS are psychometric measuring tools intended to document the characteristics of disease-related symptom severity in individuals. The neurological symptoms included in this scale are (1) extreme fatigue (2) brain fog, (3) headache (4) sleep disturbances (5) loss of taste/smell.

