All adverse events that do not meet any of the criteria for serious should be regarded as *nonserious adverse events*.

Adverse Event Reporting Period

The study period during which adverse events must be reported is typically defined as the period from the initiation of any study procedures to the end of the study treatment follow-up. For this study, treatment follow-up is described as approximately 16 weeks following the last administration of study treatment.

Stopping Rules

Infusion Stopping Rules

Study treatment infusion will be stopped if a least one of the following events occurs:

1. Allergic reaction as evidenced by severe dyspnea (defined as intense tightening of the chest, air hunger, breathlessness or feeling of suffocation), bronchospasm (defined as coughing, wheezing, difficulty breathing) or hypoxia (defined as pulse oximeter reading of less than 90%) after the product has been administered intravenously.
2. Hypersensitivity reactions such as rash, urticaria, itching, angioedema, nausea, vomiting, hypotension, or any evidence of anaphylaxis.
3. The patient verbally declines the treatment at any moment prior, or during the infusion.
4. Any febrile reaction will be an indicator for pausing the infusion for further evaluation.
5. Malignant Systolic blood pressure (SBP) greater than 170 and/or diastolic blood pressure greater than 100. SBP less than 80mm/Hg and/or DBP less than 40mm/Hg. *
6. Sudden Severe Hypotension (40 mm/Hg drop from infusion starting baseline) or systolic blood pressure <80mmHg.
7. Respiratory distress defined as having an acute sudden onset of shortness of breath or increased work of breathing, SaO₂ less than 90% or a respiratory rate >22 or < 10 breaths per minute. Any increased oxygen support that could indicate imminent respiratory failure.
8. Sudden increase or decrease in pulse rate of 30 bpm or more from infusion starting baseline or an absolute tachycardia of greater than 140 bpm or absolute bradycardia less than 45 bpm.
9. Change in neurologic status from infusion starting baseline including alertness.
10. The Principal Investigator may stop the infusion at any time, based upon PI's discretion.

*Any blood pressure from baseline exceeding or falling below $\pm 20\%$ of baseline or $\geq 140/90$ will necessitate a pause for evaluation.

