Suppose an infusion is stopped for a subject due to an adverse event or serious adverse event, including but not limited to hypersensitivity reaction/anaphylaxis. In that case, no additional study treatment will be given to the study participant who develops the event. Although the study participant will not

receive the investigational product, he or she must be followed for safety purposes according to the protocol.

Study Stopping Rules

This Clinical Trial will stop if any of the following events are present:

1. Subject's Death.
2. Any thromboembolic event will cause a pause in the study until an evaluation can be done by the DSMB, Principal Investigator and Medical Monitor to determine relationship.
3. Any cerebrovascular ischemia or seizure event occurring within 72 hours after any of the investigational product administrations.
4. Any Serious Adverse Events of the following:
 - When there is one CTCAE.v5 grade 4 or 5 AE, irrespective of attribution.
 - Either any CTCAE Grade 2 adverse event that persists for more than two weeks or any Grade 3 adverse event that occurs within 72 hours after product administration.

Should the study participant discontinue study treatment, he/she will be followed for safety according to the protocol safety monitoring plan. The study participant will receive follow-up communication via phone calls or electronically to ascertain the outcome until resolved fully. All will be documented as per protocol.

FDA shall review all changes to the study-stopping rules. If the study is suspended for any reason, it will not be re-opened until FDA agrees. Whether the study is stopped or suspended, all subjects will be followed to the EOS visit.

Statistical Methods

The sample size consists of 80 subjects who have been diagnosed with Chronic Post-COVID-19 Syndrome. All data collected from subjects who are enrolled and received the investigational product will be analyzed. The incidence of Adverse Events and Serious Adverse Events will be recorded and reported. Efficacy will be measured by improving the subject's signs and symptoms associated with Chronic Post-COVID-19 Syndrome. Interim analysis of all safety and efficacy data may be performed at any time deemed appropriate by the Sponsor. Data may be analyzed for internal informational purposes, reports, presentations, and manuscripts.

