 improvements in individual symptom scores of Visual Analog Scale of Non-Neurological Symptoms. (Time frame: Baseline to Week 26). To evaluate the efficacy of intravenous infusions of HB-adMSCs (allogeneic) vs. Placebo in patients with Chronic Post-COVID-Syndrome as determined by changes in Fatigue Scale (Time frame: Baseline to Week 26). To assess the efficacy of intravenous infusions of HB-adMSCs (allogeneic) vs. Placebo in patients with Chronic Post-COVID-19 Syndrome as determined by changes in SF-36 Quality of life self-assessment. (Time frame: Baseline to Week 26). To identify the safety of intravenous infusions of HB-adMSCs vs. Placebo in patients with Chronic Post-COVID-19 Syndrome as determined by changes in SF-36 Quality of life self-assessment. (Time frame: Baseline to Week 26). To identify the safety of intravenous infusions of HB-adMSCs vs. Placebo in patients with Chronic Post-COVID-19 Syndrome as determined by changes in fusions of HB-adMSCs vs. Placebo in patients with Chronic Post-COVID-19 Syndrome as determined by changes in fusions of HB-adMSCs vs. Placebo in patients with Chronic Post-COVID-19 Syndrome as determined by changes in Patient Health Questionnaire (PHQ-9). 	 Changes in Subject's energy and stamina as evidenced on the Fatigue Assessment form. Changes in Visual Analog Scale of non -Neurological Symptoms. The symptoms included in this scale are (1) dyspnea a rest and with activity, (2) cough, (3) body aches, and (4) joint pain. Changes in Subject's quality of life as evidenced by the Short Form 36 Health Survey Questionnaire. Changes in Subject's level of depression as evidenced by the PHQ 9 scale.

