3.2. Interim Analysis

No interim analysis planned.

Population	Definition / Criteria	Analyses
		Evaluated
Safety analysis set	 All randomized subjects who received at least one dose of HB-adMSCs infusion or placebo. If participants receive a treatment different to their randomized treatment, they will be analysed according to the treatment actually received. 	 Safety Study Population
Efficacy analysis set	 All randomized participants who received all 4 infusions of HB-adMSCs or placebo. Participants will be analysed according to their randomized treatment. 	• Efficacy
Screened Population	 This population consists of all subjects who signed an ICF to participate in the clinical trial. This population will be used for summarizing screening failures and reasons for screening failures. 	Study Population

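### PHQ-9 change is a stated safety objective, but the only PHQ-9 analysis the SAP sets out is an efficacy analysis tied to participants who received all four infusions

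*SAP*

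**What the plan says.** The protocol (Secondary Objectives) states the purpose of the PHQ-9 comparison as: "To identify the safety of intravenous infusions of HB-adMSCs vs. Placebo in patients with Chronic Post-COVID-19 Syndrome as determined by changes in Patient Health Questionnaire". SAP 2.1 carries the same objective.

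SAP 5.3.1, headed as efficacy endpoints, includes "Changes in Subject's level of depression as evidenced by the PHQ 9 scale". It applies a repeated measures model, an ANCOVA and a paired t-test, all by reference to 5.2.2. It names no analysis set.

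The analysis-set table (SAP Section 4) defines two sets that matter here:
- Efficacy, used for efficacy: "All randomized participants who received all 4 infusions of HB-adMSCs or placebo".
- Safety, used for safety and study population: "All randomized subjects who received at least one dose of HB-adMSCs infusion or placebo".

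The protocol's Infusion Stopping Rules end dosing for a participant whose infusion is stopped for an adverse event: "no additional study treatment will be given to the study participant who develops the event". The same paragraph adds that "he or she must be followed for safety purposes according to the protocol".

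The protocol's Statistical Methods section commits to analysing all data from enrolled subjects who received the product. SAP 5.4 declares no departure from the protocol's analyses.

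**The concern.** A safety question should be answered in everyone exposed. Here the only analysis spelled out for this safety objective runs in a set defined by completing treatment. Entry to that set depends on events after randomisation, and some of those events are harms. The stopping rules cover hypersensitivity, blood pressure, pulse, respiratory and neurological changes, and these could occur at different rates with cells and with saline. If people who tolerate infusions badly also do worse on mood, the PHQ-9 comparison would look more favourable than the experience of all dosed participants.

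The restriction also conflicts with the protocol's commitment to analyse all data from dosed subjects, and SAP 5.4 does not acknowledge the change.

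**Working it through.** The documents state no PHQ-9 figure, so there is none to reproduce. The check is mainly textual.

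**Step 1: which set applies to PHQ-9.** SAP 5.3.1 refers to 5.2.2 for method. Section 5.2 uses the Efficacy analysis set, and the analysis-set table pairs that set with efficacy. Nothing in 5.3.1 overrides this.

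**Step 2: what the Safety set covers.** SAP 5.3.2 covers exposure, adverse events and laboratory data. SAP 5.3.3 covers physical examination and vital signs. PHQ-9 appears in neither. SAP 5.1.1 says continuous measurements will be summarised by visit and treatment, without naming a set.

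**Step 3: who falls between the two sets.** PHQ-9 is scheduled after baseline at Weeks 2, 6, 10 and 26 (protocol Table 1). The visit procedures list it ahead of the infusion.

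| Infusion stopped for an AE | Post-baseline PHQ-9 due by then | Safety set | Efficacy set |
|---|---|---|---|
| 1 (Week 0) | none | in, if a part-given dose counts | out |
| 2 (Week 2) | Week 2 | in | out |
| 3 (Week 6) | Weeks 2, 6 | in | out |
| 4 (Week 10) | Weeks 2, 6, 10 | in | depends on whether a part-given infusion counts as received |

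So participants stopped at infusion 2 or 3 should have post-baseline scores that the stated analysis does not use.

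**Step 4: illustration of size.** From the documents: 80 subjects randomised 1:1, so 40 per arm. Everything else is assumed. Let s be the number per arm without all four infusions. Let 5% of the others worsen markedly, and let a share p of the s participants do so.

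- Safety-set rate = [s × p + (40 − s) × 0.05] / 40
- Share of worsened participants outside the Efficacy set = s × p / [s × p + (40 − s) × 0.05]

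Example: s = 4, p = 25% gives (1.0 + 1.8)/40 = 7.0%, and 1.0/2.8 = 36% outside.

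| Early stop | s | p = 5% | p = 25% | p = 50% |
|---|---|---|---|---|
| 5% | 2 | 5.0%; 5% outside | 6.0%; 21% | 7.3%; 34% |
| 10% | 4 | 5.0%; 10% | 7.0%; 36% | 9.5%; 53% |
| 20% | 8 | 5.0%; 20% | 9.0%; 56% | 14.0%; 71% |

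The Efficacy-set rate is 5.0% in every cell. The gap vanishes when stopping is unrelated to mood.

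The same effect on a mean: if three active participants worsen by 10 points and the rest do not change, the arm mean shifts by 30/40 = 0.75. If one, two or all three of them stopped early, the Efficacy-set shift is 20/39 = 0.51, 10/38 = 0.26 or 0/37 = 0. With stopping unrelated to worsening, the chance that at least one of the three is lost is 1 − (1 − q)³. That is 14%, 27% or 49% for an early-stop rate q of 5%, 10% or 20%.

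**The case against.** The sponsor has several fair replies.

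- **The SAP does not rule out a Safety-set display.** SAP 5.3.1 names no set, 5.1.1 promises summaries of continuous measurements, and the programming specification is not among the documents. This stands: the display is unstated, not precluded. But the set for a safety objective belongs in the SAP, and the only route the text gives leads to the Efficacy set.
- **The protocol introduces its secondary endpoints as covering efficacy and safety together.** So an efficacy analysis of PHQ-9 is legitimate. What is missing is the parallel safety display.
- **Adverse event reporting covers harm.** Largely true. The protocol counts any symptom that worsens during the study as an adverse event, and also abnormal results that lead to treatment or further tests. Its PHQ-9 section requires emergency action for suicidal ideation, and follow-up by the investigator where depression is found and not under care. A reader might infer that ideation or marked worsening would go unreported; the documents do not support that. The backstop is thinner late on: as SAP 5.3.2.2 is written, non-serious events starting after the last infusion are listed but not tabulated. That is a separate matter.
- **Few data may be recovered.** Someone stopped at infusion 1 has no post-baseline score by then. Later scores at infusion visits precede the stopping event. The protocol does not spell out whether PHQ-9 continues after stopping. All of this stands, and is why the table should show who has no post-baseline value.

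A reader might also infer that marked worsening goes uncounted by arm because of the choice of set. That does not follow: the SAP counts worsening in neither set, and a Safety-set mean would not count it. The objective concerns change in PHQ-9, and no document promises a threshold count.

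**Conclusion.** The point holds as a mismatch between a safety objective and the population of its only stated analysis. Followed as written, the SAP answers the PHQ-9 safety question in participants who received all four infusions. Those stopped early for an adverse event normally fall outside, contrary to the protocol's commitment on dosed subjects. The restriction affects every efficacy endpoint; what is particular to PHQ-9 is that it serves a safety objective.

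The conclusion rests on reading 5.3.1 with 5.2 and the analysis-set table, and on no PHQ-9 safety display being specified elsewhere. Its size cannot be estimated from the documents: the figures above show a mechanism under assumed rates and range from no distortion to a large one. The primary efficacy conclusion is not affected. The change should be made before unblinding because it corrects the population at almost no cost.

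**What to change.** Add PHQ-9 to SAP 5.3.3 on the Safety analysis set, by arm, descriptive only and outside the Holm procedure of SAP 3.1:

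1. Observed values and change from the SAP 5.1.2 baseline at Weeks 2, 6, 10 and 26.
2. Worst post-baseline change, including unscheduled assessments as SAP 7.2.4 allows.
3. The number in each arm with no post-baseline PHQ-9.

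Keep the mean-change models in 5.3.1, name their analysis set there, and record the restriction in SAP 5.4.

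Two additions are optional. One is a count above a single worsening threshold fixed before unblinding. The documents supply no clinical basis for a value, and a cut-off may be noisy. In a simulation of four visits with no mean change, SD of change 4 to 6 and between-visit correlation 0.3 to 0.7 (all assumed), a rise of 10 or more occurred by fluctuation in about 2.5% to 18% of participants, or 1 to 7 of 40. Such a count is for visibility, not testing: even 3/40 against 0/40 gives a two-sided Fisher p of 0.24. The other is a count of new ideation from the PHQ-9 item, if item data are stored.

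The cost of the core change is SAP wording and one table. It needs no new visits, assessments or protocol amendment.

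### PHQ-9 change is a secondary safety objective but is analysed only as efficacy, which by inference limits it to participants who received all four infusions

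*SAP*

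**What the plan says.** **Objective.** Three of the protocol's four secondary objectives concern efficacy. The fourth, on PHQ-9, begins "To identify the safety of intravenous infusions of HB-adMSCs vs. Placebo in patients with Chronic Post-COVID-19 Syndrome" and is to be judged "as determined by changes in Patient Health Questionnaire (PHQ-9)". The objectives table in SAP 2.1 carries the same safety wording.

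**Analysis.** SAP 5.3.1 (Efficacy Endpoints / Variables) lists change in the subject's "level of depression as evidenced by the PHQ 9 scale" beside the fatigue scale, the non-neurological VAS and SF-36. It then states: "Primary analysis of Repeated Measures Analysis (RMA) Model will be performed for above secondary efficacy endpoints above as given in the Section 5.2.2". ANCOVA and paired t-tests follow as further analyses.

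**Sets.** The analysis sets table (SAP Section 4) assigns efficacy to "All randomized participants who received all 4 infusions of HB-adMSCs or placebo", grouped as randomized. It assigns safety to everyone with at least one dose, grouped by treatment received. SAP 5.2 names the efficacy set for the primary endpoint. SAP 5.3.2 names the safety set for safety analyses.

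**Stopping.** When an infusion is stopped for an adverse event, the protocol's Infusion Stopping Rules say "no additional study treatment will be given to the study participant who develops the event", and the participant stays under safety follow-up.

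**General rule.** The protocol's Statistical Methods section commits to analysing the data of every enrolled subject who received product. SAP 5.4 declares no departure from the protocol's analyses.

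**The concern.** A safety comparison should cover everyone who was exposed. The four-infusion set is defined by what happens after randomization, and treatment itself can cause someone to miss an infusion. If PHQ-9 is compared only in that set, the between-arm result describes people who went through the full course. Mood scores from those who did not are left out, even where they were collected.

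The label also affects multiplicity. SAP 3.1 applies Bonferroni-Holm to the secondary efficacy endpoints. As an efficacy endpoint, PHQ-9 counts toward the number of hypotheses; as a safety measure, its place there needs a decision.

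**Working it through.** The plan states no figure on this point, so the check is mainly a reading of the text. The arithmetic in steps 4 and 5 only illustrates the size.

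**1. From objective to analysis set.**

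| Step | Source | Result |
|---|---|---|
| Purpose of PHQ-9 | Protocol, Secondary Objectives; SAP 2.1 | Safety |
| Where it is analysed | SAP 5.3.1 | Efficacy, by the models of 5.2.2 |
| Set named in 5.3.1 | SAP 5.3.1 | None |
| Set for efficacy | Analysis sets table; SAP 5.2 | All four infusions received |
| Listed safety analyses | SAP 5.3.2 to 5.3.3 | Exposure, adverse events, laboratory data, physical examination, vital signs; no PHQ-9 |

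The four-infusion restriction is thus an inference. It is the only route the text offers, because nothing places PHQ-9 in the Safety analysis set.

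**2. Who is left out.** Any dosed participant who misses an infusion, for any reason. This includes anyone stopped for an adverse event at infusion 1, 2 or 3. Someone stopped during infusion 4 may still count, since the table does not say whether a partial infusion counts as received. Someone who withdraws after infusion 4 stays in the set, though the Week 26 value may be missing.

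**3. Whether their data exist.** Table 1 of the protocol schedules PHQ-9 at screening, baseline and Weeks 2, 6, 10 and 26. In the visit procedures the questionnaires are listed before the infusion. A participant stopped at infusion 3 (Week 6) would therefore normally already have Week 2 and Week 6 scores. Later scores may exist, because follow-up continues, but the protocol does not say which questionnaires are completed after stopping.

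**4. How many.** Inputs: N = 80 (both documents), 1:1 allocation (SAP 2.2), and an assumed share s who miss an infusion. Excluded = 80 × s.

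- s = 5%: 80 × 0.05 = 4, leaving 76
- s = 10%: 80 × 0.10 = 8, leaving 72
- s = 15%: 80 × 0.15 = 12, leaving 68

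**5. When the comparison is biased.** Let D be the extra PHQ-9 worsening in early stoppers relative to those with four infusions. In one arm, the mean change over all dosed participants exceeds the four-infusion mean by s × D. The between-arm difference (HB-adMSCs minus placebo) therefore shifts by

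s(active) × D(active) − s(placebo) × D(placebo).

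Assume D = 3 to 5 points and a PHQ-9 value for every stopper:

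- 5% in both arms, same D: 0
- 10% active, 5% placebo: 0.10 × 3 − 0.05 × 3 = 0.15, up to 0.10 × 5 − 0.05 × 5 = 0.25
- 15% active, 5% placebo: 0.45 − 0.15 = 0.30, up to 0.75 − 0.25 = 0.50
- 20% active, 5% placebo: 0.60 − 0.15 = 0.45, up to 1.00 − 0.25 = 0.75
- 5% in both arms, extra worsening only in active stoppers: 0.05 × 3 = 0.15, up to 0.05 × 5 = 0.25

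A shift needs unequal stopping or unequal worsening. Neither its size nor its direction can be known from the documents.

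**The case against.** **Section 5.3.1 names no set.** True. The sentence in SAP 5.2 that names the efficacy set concerns the primary endpoint. SAP 5.1.1 also promises by-visit summaries of continuous measurements without naming a set. If the sponsor always meant the safety set for PHQ-9, nothing in the SAP says so, and the gap still has to be closed.

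**PHQ-9 may serve as efficacy.** The endpoint list is headed jointly as efficacy and safety and does not label PHQ-9, so the mismatch could be closed by rewording the objective. But the objective is explicit in both documents, and under the protocol's amendment section changing it needs FDA and IRB agreement. If PHQ-9 serves both purposes, the safety purpose still lacks an analysis in all dosed participants.

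**Worsening is not hidden.** A reader might infer that the plan conceals depression in early stoppers. The documents do not support that. Symptoms that develop or worsen are adverse events. The protocol's PHQ-9 section requires follow-up of depression and emergency evaluation of suicidal ideation. Adverse events are reported in the Safety analysis set. What is lost is narrower: the between-arm comparison of scores among those who stopped.

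**Not all those excluded are adverse-event cases.** A reader might also infer that they are. Voluntary withdrawal, declining an infusion, or failing the pre-infusion vital-sign limits can each cost an infusion. Adverse-event stops are a subset of unknown size.

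**The root is the four-infusion set itself.** It affects every efficacy endpoint. If it were replaced by all dosed participants, the exclusion here would go and a labelling mismatch would remain. That is fair, but the PHQ-9 repair does not depend on that change, because the set it needs is already defined.

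**Conclusion.** The point holds. PHQ-9 change is a safety objective with no planned safety analysis, and the only analysis the SAP gives it leads, by inference, to the four-infusion set. Followed as written, the plan departs from the protocol's commitment to analyse all treated subjects, while SAP 5.4 says there is no departure.

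The size is uncertain. With 5–15% assumed to miss an infusion, 4–12 of 80 leave the comparison. The between-arm difference does not move if stopping and worsening are alike in the two arms. Under the assumed unequal scenarios it moves by 0.15 to 0.75 PHQ-9 points.

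A reader might infer a calculable loss of power from keeping PHQ-9 in the Holm family. The documents do not allow that calculation: they give no effect size or SD, and the number of hypotheses is not stated. It could be 4 (one per instrument) or 14 (1 fatigue score + 4 VAS symptoms + 8 SF-36 dimensions + 1 PHQ-9). The multiplicity question is one to settle along with the label, not a separate defect.

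**What to change.** Move PHQ-9 to SAP 5.3.2 or 5.3.3, with wording such as:

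> Change from baseline in PHQ-9 will be compared between arms in the Safety analysis set, by treatment received, using all available post-baseline values whether or not infusions continued. Results limited to participants with all four infusions are supportive only.

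In SAP 3.1, state whether PHQ-9 remains in the Holm family once it is classed as safety, and list the hypotheses that do belong to it.

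The cost is SAP wording and a change of population for one table. The set already exists, no new data are needed, and the protocol objective stands. The change should be made before database lock.
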